4.3.4. Definition of Baseline

Baseline is defined as the last available assessment prior to the first intake of IP. For the parameters for which the time of assessment was planned to be collected, if for their assessment on the day of first intake the time is missing, their assessment at time point “PRE-DOSE” (when applicable) will be considered as baseline, otherwise, previous days last available assessment will be selected. For the parameters for which the time of assessment was not planned to be collected, their assessment on the day of first intake of IP will be considered as baseline. If multiple values on the same day qualify as last available assessment, the average of these values will be used in the analysis.

For ECG data assessed in triplicate, baseline is defined as the average (stored without rounding) of the combination of the most complete replicated ECG parameter before first intake of IP and at the same time the closest to it, selecting in the following order:

First consider Day 1, pre-dose:

- Select the average of the last available triplicate ECG parameter on that day;
- If there is no triplicate, select the average of the last available duplicate ECG parameter;
- In the absence of triplicates and duplicates the last available single ECG parameter will become baseline.

If baseline is not yet determined, consider the previous day and repeat the above selection (average of last triplicate, average of last duplicate, last single ECG on that day). Repeat the whole process successively for each previous day(s) as needed until baseline is determined.

4.3.5. Selection and Use of Analysis Visits

Before first administration of IP, only Baseline will be used for the entire statistical analysis. Pre-baseline assessments will only be listed. After first administration of IP, if multiple valid, non-missing assessments exist in an analysis window, records will be chosen based on the following rules if a single value is needed:

- The record closest to the nominal day for that visit will be selected, or
- If there are 2 records that are equidistant from the nominal day, or more than 1 record (with time known) on the selected day, the latest record will be taken
- If chronological order cannot be determined (e.g., more than 1 record on the same day with time missing), the average of the records will be computed and reported in the analysisFor the composite endpoints including DAS28 (CRP), [REDACTED], the following steps will be used to derive [REDACTED], unless otherwise specified:
- Step 1: Put [REDACTED] component value into an analysis visit window.

- Step 2: Within each visit window, select the data points for analysis.
- Step 3: Combine these selected data points within each analysis visit window across the components

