8.1. Timing of Assessments

The study assessments will be undertaken at time points as specified in the Schedule of Activities in Section 8.11. At Visit 1, 3, 5, and if applicable the ED visit, subjects need to come for the study visits in a fasting state (no food intake for at least 8 hours).

ICF needs to be signed before any study procedure, including screening procedure, is carried out.

The sequence of study assessments will preferably be as follows when planned at the same time point:

1. Patient Questionnaires: Patients's Global Assessment of Disease Activity and Patient-Reported Functional Status and Pain
2. Investigator Questionnaires and joint counts
3. 12-Lead ECG
4. Vital signs
5. Blood sampling for clinical laboratory assessments and PK

The following collection time windows apply:

- 12-Lead ECGs, vital signs and physical examinations: within 3 hours predose.
- Urine sampling for clinical laboratory safety: any time predose, on the same visit day, and 2 hours postdose on visits 1 and 5.
- 
- Blood sampling for PK determination of GLPG3970:
 - Visit 1, 3, 4 and 5: within 30 minutes predose.
 - Visit 1: 1 sample within [0.5-1.5 hours postdose] and 1 sample within [2-2.5 hours postdose].
 - Visit 5: 1 sample within [4-6 hours postdose].
- 

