8.5.2. Clinical Laboratory Evaluations

The following clinical laboratory safety tests will be performed:

- **Hematology:** hematocrit, hemoglobin, red blood cell count, white blood cell count, white blood cell differential count (absolute and relative), mean corpuscular volume (MCV), mean corpuscular hemoglobin (MCH), mean corpuscular hemoglobin concentration (MCHC), red blood cell distribution width and platelets.
- **Coagulation:** INR (only when increase in LFTs, see Section 6.4), activated partial thromboplastin time and prothrombin time.
- **Clinical chemistry:** glucose, urea, creatinine, uric acid, sodium, potassium, calcium, reflex calcium (free/ionized; only if serum calcium total is elevated), chloride, phosphorus, AST, ALT, GGT, total bilirubin, alkaline phosphatase (ALP, ALP fractions only if ALP is elevated), creatine phosphokinase, lipase, amylase, lactate dehydrogenase, insulin, hemoglobin A1c (HbA1c), albumin, total proteins, triglycerides, cholesterol, high-density lipoprotein (HDL), low-density lipoprotein (LDL), and hsCRP. Homeostatic model assessment of insulin resistance (HOMA-IR, see [Definition of Terms](#)) and HDL/LDL ratio will be derived from clinical chemistry parameters. An estimate of the

ClCr based on the serum creatinine level will be calculated by the central laboratory using the Cockcroft-Gault formula (see [Definition of Terms](#)).

– **Urinalysis:**

Dipstick: pH, glucose, proteins (qualitative), blood, leukocytes, ketones.

Microscopic examination of the sediment for cellular elements (cylinders, erythrocytes, leukocytes), if indicated (when the test strip was positive for blood and/or proteins).

Quantitative urine proteins, only when the test strip was positive for proteins.

Calcium, phosphate, creatinine and N-acetyl- β -D-glucosaminidase (NAG). The urine protein to creatinine ratio will be derived.

– **Serology:**

HBsAg and hepatitis C antibody, and HIV 1 and 2 (at screening). Positive hepatitis and HIV results should be reported by the investigator as required by local law.

– FSH test for females at screening to confirm menopause if applicable

– **Pregnancy test for females:**

serum beta human chorionic gonadotropin at screening, baseline (Visit 1), at Visit 4 (Day 29) and at Visit 5 (Day 43), , or the ED visit, if applicable (all female subjects).

– **QuantiFERON-TB Gold test** to check for latent or active TB (at screening). TB results should be reported by the investigator as required by local law.

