⁵ Height only to be measured at screening.⁶ RT-PCR from a nasal swab sample at screening and RT-PCR from a nasal swab sample and serology testing at baseline (Visit 1), and as needed when subject presents signs and symptoms of SARS-CoV-2 infection.⁷ Fasted glucose, fasted insulin and HOMA-IR only at Visit 1, 3 and 5 and the ED visit, if applicable.⁸ On dosing days, clinical safety urine samples will be taken predose, on the same visit day.⁹ Visit 1 and 5: predose and 2 hours postdose. Calcium and phosphate should only be evaluated at Visits 1 and 5.

EVENT	SCREENING PERIOD	TREATMENT PERIOD ^{1,2}						FOLLOW-UP PERIOD ²
		1	2	3	4	5	ED ³	
Study visit	S	1						FU Visit
Study Weeks		Baseline	1	2	4	6		
Study Day (D) ± Days	-21 to -1	1	8 ± 2	15 ± 2	29 ± 2	43 ± 2	Early treatment discontinuation	57 ± 3
PK blood samples for GLPG3970		✓ ¹⁰		✓ ¹¹	✓ ¹¹	✓ ^{11,12}	✓	
		✓		✓	✓			
		█		█		█		█
		█		█		█		
		█		█		█		
Subject diary evaluation		✓	✓	✓	✓	✓	✓	✓
SJC66/TJC68	✓	✓	✓	✓	✓	✓	✓	
	█	█	█	█	█	█	█	

¹⁰ Visit 1: predose (within 30 minutes prior to dosing), 1 sample within [0.5-1.5 hours postdose] and 1 sample within [2 – 2.5 hours post dose].

¹¹ Visit 3, 4 and 5: predose (within 30 minutes prior to dosing).

¹² Visit 5: 1 sample within [4-6 hours postdose].

¹³

EVENT	SCREENING PERIOD	TREATMENT PERIOD ^{1,2}						FOLLOW-UP PERIOD ²
		1	2	3	4	5	ED ³	
Study visit	S	1						FU Visit
Study Weeks		Baseline	1	2	4	6		
Study Day (D) ± Days	-21 to -1	1	8 ± 2	15 ± 2	29 ± 2	43 ± 2	Early treatment discontinuation	57 ± 3
Dispense IP		✓ ¹⁵		✓ ¹⁵	✓ ¹⁵			
IP administration ¹⁵		Once daily throughout the treatment period						
AE and concomitant medication		throughout the study						

¹⁵ On Visit 1, 3, 4 and 5 administration of IP must occur at site.

[figure not shown]

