4.3. Analysis Periods and Analysis Time Points

4.3.1. Relative Day

The timing of an assessment or an event relative to a reference date will be calculated as follows:

When the concerned date is before the reference date:

$$\text{Relative day (days)} = \text{concerned date} - \text{reference date}$$

When the concerned date is the equal to or later than the reference date:

$$\text{Relative day (days)} = \text{concerned date} - \text{reference date} + 1 \text{ day}$$

where:

- The *concerned date* could be the measurement date of the assessment, or the start or end date of the event.
- The *reference date* default is the date of the first dose of IP administration, unless specified otherwise.
- *Date* implies a complete date having day, month and year available. Unless otherwise specified, the *relative day* will remain missing when it cannot be calculated due to absence or incompleteness of the concerned and/or reference dates.

The general terms of this formula also apply when similar relative timings are required in other time units, for example in minutes.

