4.3.3. Analysis Windows

For the efficacy, PK, [REDACTED] and safety assessments, all data (including data obtained at unscheduled visits) will be placed into time windows based on the relative day (ADY) of the assessment (relative to the first dose of IP), according to the following allocation tables:

For endpoints with multiple components, analysis windows will be derived separately for each component/parameter.

Table 2: Analysis Visit Window for non-PK data

Visit date and time	Relative day (ADY)	Assessment visit (VISIT)	Time window (in ADY)	Target day	Analysis visit (AVISIT)
On or before first study drug administration	≤ 1	Last assessment at any point in time before first study drug administration	≤ 1	1	Baseline
After first study drug administration	>1	Any scheduled (non follow-up), unscheduled, or early discontinuation visit	2 to 12	8	Week 1
			13 to 22	15	Week 2
			23 to 36	29	Week 4
			37 to 49	43	Week 6
		Follow-up	CRF collected follow-up visit		Follow-up

Table 3: Analysis Visit Window for PK data

Visit date and time	Relative day (ADY)	Assessment visit (VISIT)	Time window (in ADY)	Target day	Analysis visit (AVISIT)	Analysis time point (ATPT)
Before first study drug administration	<1 or pre-dose at ADY=1	Last assessment at any point in time before first study drug administration	<1 or pre-dose at ADY=1	1	Baseline	Pre-dose (within 30 minutes prior to dosing)
Same as or after first study drug administration	≥ 1	Any scheduled (non follow-up), unscheduled, or early discontinuation visit	1	1	Day 1	As indicated in the database: 0.5-1.5, 2-2.5 hours post-dose
			13 to 22	15	Week 2	As indicated in the database: Pre-dose (within 30 minutes prior to dosing)
			23 to 36	29	Week 4	As indicated in the database: Pre-dose (within 30 minutes prior to dosing)
			37 to 49	43	Week 6	As indicated in the database: Pre-dose (within 30 minutes prior to dosing) and within [4-6 hours post dose].

Visit date and time	Relative day (ADY)	Assessment visit (VISIT)	Time window (in ADY)	Target day	Analysis visit (AVISIT)	Analysis time point (ATPT)
		Follow-up	CRF collected follow-up visit		Follow-up	

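### For quantitative urine tests with timed samples, the same-day rule sets a 2-hour post-dose Week 6 value against a pre-dose baseline, and the Day 1 post-dose sample has no analysis window

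*SAP*

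**What the plan says.** **Sampling.** Protocol 8.1 sets "Urine sampling for clinical laboratory safety: any time predose, on the same visit day, and 2 hours postdose on visits 1 and 5". Footnote 9 of the SAP 2.5 schedule agrees: "Visit 1 and 5: predose and 2 hours postdose. Calcium and phosphate should only be evaluated at Visits 1 and 5". Footnote 15 of the same schedule says "On Visit 1, 3, 4 and 5 administration of IP must occur at site", so the second sample follows an actual dose.

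**Tests.** Protocol 8.5.2 lists urine calcium, phosphate, creatinine and NAG, and quantitative protein when the dipstick is positive. It adds: "The urine protein to creatinine ratio will be derived".

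**Baseline.** SAP 4.3.4 uses the final value before the first dose. The Baseline row of SAP Table 2 (section 4.3.3) likewise admits only the "Last assessment at any point in time before first study drug administration".

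**Windows.** Table 2, for non-PK data, is indexed by relative day alone, and its rows after baseline begin at relative day 2. Table 3, for PK data, has a Day 1 row and a column for analysis time point.

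**Selection.** Where one value per window is needed, SAP 4.3.5 takes the record nearest the nominal day. With "more than 1 record (with time known) on the selected day, the latest record will be taken". Same-day records whose order cannot be established are averaged. SAP 4.3.6.1 omits assessments with a missing date (time) from by-visit summaries.

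**Reporting.** SAP 6.3.2.9 summarises continuous laboratory tests by analysis window as actual value, change and percent change.

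**The concern.** A change from baseline should compare like with like. Here one side of the subtraction is fixed as pre-dose, and a general tie-breaking rule makes the other side post-dose. The rule looks as though it was written for repeat or unscheduled records on a day, not for two scheduled samples that differ by design.

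It matters most for urinary calcium and phosphate, which are evaluated only at Visits 1 and 5. No other scheduled treatment visit supplies a pre-dose change for them. A reader of the Week 6 table could take a shift that arises within hours of a dose, or from a later collection time, for the result of six weeks of treatment. An acute shift in the opposite direction could equally hide a real 6-week change.

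**Working it through.** The plan states no figure on this point, so the check applies its rules to the scheduled samples.

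**Step 1: relative day.** SAP 4.3.1 covers this case: "When the concerned date is the equal to or later than the reference date", the day number is the date difference plus 1. Both Day 1 samples therefore have relative day 0 + 1 = 1.

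**Step 2: window and selection.** The Week 6 window is days 37 to 49, with target day 43. Visit 5 is Day 43 ± 2, that is, Days 41 to 45.

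| Sample | Relative day | Table 2 window | In by-window summary |
|---|---|---|---|
| Visit 1, pre-dose | 1, before dose | Baseline | Yes |
| Visit 1, 2 h post-dose | 1, after dose | None: not before dose, and later rows start at day 2 | No |
| Visit 5, pre-dose | 41 to 45 | Week 6 | No: earlier record on the day |
| Visit 5, 2 h post-dose | 41 to 45 | Week 6 | Yes: latest record on the day |

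On any of Days 41 to 45 the two Visit 5 samples share a date, so they are equally far from day 43 and the same-day rule decides. Two of the four planned samples feed the summary.

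**Step 3: what the reported change contains.** Write U for the urine value. Then

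U(Week 6, post) − U(Day 1, pre) = [U(Week 6, pre) − U(Day 1, pre)] + [U(Week 6, post) − U(Week 6, pre)].

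The first bracket is the like-for-like 6-week change. The second is the acute post-dose and time-of-day change. The documents give no value for the second bracket, so neither its size nor its sign can be stated.

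**Step 4: number of subjects.** The plan is to randomise 25 subjects with 20% dropout, and 25 × (1 − 0.20) = 20 completers. If all give both Visit 5 samples with times, about 20 to 25 subjects are affected for each test.

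**Step 5: cases where the rule acts differently.**
- Visit 5 times missing: 4.3.5 averages the two values, which leaves half of the second bracket in the change. Under 4.3.6.1 they may instead be omitted.
- Post-dose sample not taken: the pre-dose value is used, and the comparison is like for like.
- Early discontinuation visit in the window with a single sample, for example on Day 40: that sample is used.

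**The case against.** Much can be said on the other side.

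- **Scope.** A reader might infer that every Week 6 urine value is post-dose. The documents do not support that. The rule applies only where a single value is needed, and Step 5 gives exceptions. SAP 6.3.2.5 tabulates qualitative urinalysis by time point, which may keep the two samples apart.
- **Discarded data.** A reader might infer that the unselected samples are lost. They are not. SAP 6.3.2.9 plans listings and subject profile plots of all observed values. Both samples fall in the Treatment period (SAP 4.3.2) and can enter the worst-case tables of SAP 6.3.2.7 where a grade or laboratory flag exists.
- **A planned comparison.** A reader might infer that a planned Day 1 pre/post comparison disappears. The documents schedule the paired samples, but no visible text plans an analysis of the pair.
- **Whether times are recorded.** Neither document says whether urine times are captured. If they were never planned, SAP 4.3.4 takes the Day 1 assessment as baseline and averages qualifying same-day values. Both visits could then be pre/post averages. The mismatch would largely go, but baseline would contain a post-dose value.
- **Consequence.** These are descriptive safety summaries without formal tests, and both arms follow the same rule.
- **Unseen text.** SAP section 1 places derivation details in a separate document, and much of SAP 6.5 is redacted. Either might hold a time-point rule.

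All of this stands as a limit on scope. None of it supplies a pre-dose Week 6 summary where both samples are timed, which is what the schedule would lead one to expect.

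**Conclusion.** The point holds for quantitative urine tests with both Visit 5 samples taken and timed. For these the stated rule produces a post-dose minus pre-dose change, and the Day 1 post-dose sample has no Table 2 window. This is a written rule giving a mismatched result, not just missing detail.

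The effect is confined to by-window descriptive summaries. The Week 6 comparison between arms remains randomised, but it is a comparison at 2 hours after dosing, which the SAP does not say it intends. The within-arm change is the quantity that becomes hard to interpret. The primary endpoint (DAS28 change), the secondary endpoints (TEAEs and trough concentrations), the sample size and the decision framework are untouched.

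The conclusion assumes that urine times are recorded and that no rule in the redacted text or the derivations document overrides SAP 4.3.5.

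**What to change.** In SAP Table 2, add an analysis time point for urine, as Table 3 has for PK, with four entries: Baseline pre-dose, Day 1 at 2 hours post-dose, Week 6 pre-dose, and Week 6 at 2 hours post-dose.

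In SAP 4.3.5, apply the latest-record and averaging rules only within a time point. In SAP 6.3.2.9, compute the Week 6 urine change from baseline from the pre-dose sample and summarise the post-dose values separately. State whether urine collection times are recorded. If a time is missing, use the nominal pre-dose or post-dose label, as SAP 4.3.4 already does for baseline. If the derivations document already contains such a rule, a cross-reference is enough.

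The cost is SAP wording and programming, to be settled before database lock and unblinding. No new data or visits are needed.

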4.3.6. Handling of Missing Data

4.3.6.1. Handling of Missing Date-Time Data

No imputations will be done in case of missing date (time) fields, nor for the missing parts of partially known date (time) fields.

Assessments with missing date (time) will be omitted from the summaries by visit.

Event-type data (e.g. AEs, concomitant medications) with missing date (time) will be allocated to analysis periods using a worst-case approach as explained in the respective sections.

4.3.6.2. Handling of Missing Result Data

No imputation will be done of missing result data unless otherwise specified. That is, an observed case (OC) analysis will be performed unless otherwise specified. Endpoints analyzed via mixed models for repeated measures (MMRM) handle missing data via the maximum-likelihood function.

For some binary endpoints, missing data will be handled using both an OC approach and non-responder imputation (NRI) as specified in [Section 6.2](#). NRI being the imputation of missing values by a non-response/non-remission.

4.3.6.3. Censoring of Time to Event Data

Not applicable.

4.3.7. Handling of Values Below or Above a Threshold

Results of continuous parameters, as well as normal limits of these reported as below (or above) the detection limit will be imputed by the value one precision unit smaller (or larger) than the detection limit itself. In listings, the original value will be presented.

Example: if the database contains the value “<0.04”, then for the descriptive statistics the value “0.03” will be used. The value “>1000” will be imputed by “1001”.

For PK data, values below the limit of quantification will be imputed by 0 for the calculation of descriptive statistics presentation; except for the geometric mean and the geometric CV%, where it will be imputed as LLOQ/2. These values will be listed as “below lower limit of quantification (BLOQ)”.

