4.4.2. Calculation of Descriptive Statistics

For continuous parameters, descriptive statistics will be presented when $N \geq 2$. When $N = 1$, the observation will not be shown in tables nor in figures of summary statistics but will only be listed.

Descriptive statistics will include:

- the number of non-missing data points (n);
- the arithmetic mean;
- the standard error (SE) and standard deviation (SD);

- the median, minimum and maximum;
- 90% confidence interval (CI) of the mean (if indicated in the relevant section).
- Some parameters namely hsCRP, cytokines (IL-10 and TNF α) and metabolic parameters (fasted insulin, HOMA-IR and HbA1c) are known to deviate heavily from the normal distribution but follow the log-normal distribution well. For these parameters, the geometric mean (GeoMean), geometric standard deviation (GeoSD), and geometric standard error (GeoSE) will be also reported for the summaries by treatment group and visit. GeoMean, GeoSD and GeoSE are not applicable for the summaries of the changes from baseline, however GeoM, GeoSD and GeoSE will be reported for the summaries of percent changes from baseline. This will be done by obtaining the mean, GeoSD and GeoSE of $\log(\text{value}) - \log(\text{baseline})$ and then transforming these statistics back to the 'percent change scale' as $100 \times \{\text{exponential}(\text{statistic}) - 1\}$.

For PK data, descriptive statistics will include:

- the number of non-missing observations (n);
- the number of data points above the LLOQ;
- the arithmetic mean;
- SE and SD;
- the median, minimum and maximum;
- the coefficient of variation (CV%);
- the geometric mean and geometric CV%.

If less than 50% of the subjects have quantifiable values, only the number of subjects with data, number of data points above the LLOQ, the arithmetic mean, median, minimum, and maximum will be presented with the original calculated value. The other descriptive statistics will be listed as "NC" (not calculated).

If the calculated descriptive statistic is BLOQ, then it will be presented as "BLOQ".

Individual values and descriptive statistics of concentrations and PK parameters will be presented with 3 significant digits.

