6.5.2. Presentation of Results

All continuous parameters mentioned in section 6.5.1 will be summarized by means of descriptive statistics (including 90% CI of the mean change from baseline) by treatment group and analysis window. Actual values, changes from baseline and percent change from baseline will be tabulated separately.

Between-group comparisons will be based on the percent change from baseline, and will present a p-value and 90% CI of the delta between GLPG3970 and placebo. The same MMRM approach as for the efficacy endpoints will be applied.

Graphs of the mean (+- SE) actual values over time and of the mean (+- SE) change from baseline, and percent changes from baseline will be presented for all continuous parameters. Also, linear-linear plots for actual values will be provided by treatment group. In addition, profile line plots of the percent change from baseline will be provided by treatment group.

For cytokines and metabolic markers mentioned under section 6.5.1, the analysis of percent change from baseline will be performed as described in section 4.5.2. The same MMRM approach as detailed in [section 6.5.1.2](#) will be applied. The GeoLSM and GeoSE and corresponding 90 % CI will be presented (the same back transformation to the 'percentage scale' as for the geometric descriptive statistics will be applied to the LS-mean, SE and corresponding 90% CI bounds). The GeoMean (\cdot/\div GeoSE) of the actual values and percent changes from baseline will be presented graphically over time on a log-linear scale. Error band will be calculated as follows:

- Error bands: $100 \times [\text{exponential} \{ \text{mean} (Z) \pm \text{SE} (Z) \} - 1]$. Where $Z = \log (\text{value}) - \log (\text{baseline})$.

Listings will be provided for all cytokines, bone markers and metabolic markers separately. Column includes the actual values, change from baseline and percent change from baseline, and also a flag for high/low values in case a normal range exists.

Note: HOMA-IR values will be excluded from analysis if samples are not taken fasted (i.e. "fasted" is explicitly mentioned in the database),

6.6.

[REDACTED]

[REDACTED]

[REDACTED]

[REDACTED]

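### SAP 4.3.7 can set a below-limit marker result to zero, which leaves the planned log-ratio analysis undefined for that record

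*SAP*

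**What the plan says.** **Threshold rule.** SAP 4.3.7 covers continuous results reported as below or above the detection limit. The result "will be imputed by the value one precision unit smaller (or larger) than the detection limit itself". In the SAP's example, for a database entry of `<0.04`, "then for the descriptive statistics the value" 0.03 is used, and `>1000` becomes 1001. The rule sets no floor above zero and does not distinguish linear from log-scale use.

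**PK exception.** For PK data the same section uses 0 for descriptive statistics, "except for the geometric mean and the geometric CV%, where it will be imputed as LLOQ/2". This exception is not extended to any other parameter.

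**Log-scale summaries.** SAP 4.4.2 names hsCRP, IL-10, TNF-alpha, fasted insulin, HOMA-IR and HbA1c. It says that they "are known to deviate heavily from the normal distribution but follow the log-normal distribution well". It plans geometric means, SDs and SEs of the values. Percent change is summarised through log(value) − log(baseline) and back-transformed as 100 × {exp(statistic) − 1}.

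**Log-scale model.** SAP 6.5.2 states: "For cytokines and metabolic markers mentioned under section 6.5.1, the analysis of percent change from baseline will be performed as described in section 4.5.2". In the current numbering that text stands in 4.4.2. An MMRM follows, with geometric LS means and 90% CIs.

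**Missing results.** SAP 4.3.6.2: "No imputation will be done of missing result data unless otherwise specified". MMRM endpoints rely on the likelihood.

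**The concern.** The threshold rule and the log-scale analyses do not fit together. The rule can produce zero, the log analyses need a strictly positive number, and no readable passage says what happens when they meet. In practice an undefined log becomes a missing response, and the plan does not impute missing results.

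That loss depends on the value itself, so the missing-at-random argument behind the MMRM does not cover it. The mechanism of action in the protocol introduction is expected to lower TNF-alpha, so the post-baseline TNF-alpha values lost would tend to be the largest reductions, and the estimated reduction would shrink. The same direction applies to hsCRP. IL-10 is expected to rise, so its likelier problem is a result below the limit at baseline. A zero baseline makes every log-ratio for that subject and marker undefined.

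Losing such records also sits badly with SAP 4.3.8, under which all measured values are included. That the SAP protects geometric PK statistics against zero suggests that the marker case was overlooked rather than chosen.

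**Working it through.** **1. The SAP's example.** Imputed value = limit ∓ one unit in the last printed place.
- `<0.04`: 0.04 − 0.01 = 0.03.
- `>1000`: 1000 + 1 = 1001.

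Both agree with SAP 4.3.7.

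**2. When the rule gives zero.** It does so exactly when the limit equals one unit in its last printed place. The baseline of 15 below is assumed, for illustration only.

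| Reported | Imputed by 4.3.7 | ln(imputed/15) | Half the limit | ln(half/15) |
|---|---|---|---|---|
| `<0.01` | 0.00 | undefined | 0.005 | −8.006 |
| `<0.04` | 0.03 | −6.215 | 0.02 | −6.620 |
| `<0.1` | 0.0 | undefined | 0.05 | −5.704 |
| `<0.10` | 0.09 | −5.116 | 0.05 | −5.704 |
| `<1` | 0 | undefined | 0.5 | −3.401 |
| `<1.0` | 0.9 | −2.813 | 0.5 | −3.401 |
| `<2` | 1 | −2.708 | 1 | −2.708 |

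The same limit can be defined or undefined depending only on the number of decimals printed (`<1` against `<1.0`).

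**3. How many values could be lost.** The documents give no assay limits or marker distributions, so every input here is an assumption except the 15 active subjects (SAP 2.3). Assume a baseline geometric mean of 15, a log-SD of 0.6 at baseline and 1.0 for change, and a mean log change δ. Post-baseline logs then have mean ln 15 + δ and SD √(0.6² + 1.0²) = 1.166.

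For δ = −1.6 the mean is 2.708 − 1.6 = 1.108. The expected number below the limit is:
- limit 1: 15 × Φ((0 − 1.108)/1.166) = 15 × Φ(−0.950) ≈ 2.6;
- limit 0.1: 15 × Φ((−2.303 − 1.108)/1.166) = 15 × Φ(−2.925) ≈ 0.03.

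**4. Effect on the estimate.** Simulated mean at one visit, 4,000 repeats, with results below the limit treated as zero and dropped. Percentages are 100 × {exp(mean) − 1}.

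| Limit | δ | Mean number lost of 15 | All true values | Lost values dropped | Half the limit |
|---|---|---|---|---|---|
| 0.1 | −1.6 | 0.03 | −79.8% | −79.7% | −79.9% |
| 1 | 0 | 0.15 | 0.0% | +2.4% | −0.3% |
| 1 | −1.0 | 1.06 | −63.0% | −58.1% | −63.5% |
| 1 | −1.6 | 2.58 | −79.8% | −73.7% | −80.1% |

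These are simple means at one visit. An MMRM would recover some information from a subject's other visits.

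**5. The primary endpoint.** DAS28 (CRP) uses 0.36 × ln(1 + CRP) (SAP 6.2.2.1), which is defined at CRP = 0. The imputed number still enters it. For an assumed limit of 1:
- `<1` gives 0.36 × ln(1) = 0;
- `<1.0` gives 0.36 × ln(1.9) = 0.231;
- half the limit gives 0.36 × ln(1.5) = 0.146.

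A remedy applied to hsCRP as a parameter, rather than to the log analyses, would therefore move a primary-endpoint score by +0.146 or by 0.146 − 0.231 = −0.085.

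**The case against.** **It is hypothetical.** Zero needs a particular match between limit and printed precision, and the SAP's only low-end example stays positive. This stands as a limit on size. A reader might infer that records will be lost, or that the log analyses will fail; the documents support only that they can.

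**Marker-specific rules may sit in unreadable text.** Much of SAP 6.2.3 and 6.5 is blacked out, including where a model for hsCRP would be expected, and SAP section 1 places technical derivations in a separate document. That is why the point is confined to readable text: for hsCRP it rests on the summaries in 4.4.2. It does not remove the point, because the general rule and the log-scale text are both readable and neither sets a floor.

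**Not all six markers are at risk.** A reader might infer that every listed marker is affected, or that the lost records are always those with the strongest suppression. HbA1c is graded from 6.0 upward in SAP Appendix I and will not approach a detection limit. HOMA-IR is a product and becomes zero only through insulin. IL-10 is expected to rise. Screening hsCRP must exceed an upper limit of normal of 5.0 mg/L, so an undetectable baseline is unlikely. If hsCRP is printed to one decimal, as that reference value is, zero needs a `<0.1` result. From 5.0 that is a fall of at least 1 − 0.1/5.0 = 98%.

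**A lost record is not a lost subject.** One lost post-baseline record is 1/15 = 6.7% of the active arm at that visit only. With three post-baseline visits, as in the primary MMRM, it is 1/45 of the arm's records. Only a zero baseline removes the subject, and then for that marker alone.

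**Half the limit is also a convention.** This stands. It is single-value substitution and can produce an influential point. With 14 assumed log-ratios of −1.6 and one of −5.704, the mean is (14 × −1.6 − 5.704)/15 = −1.874, or −84.6% instead of −79.8%. Most of that pull is real, however, because any true value below 0.1 has a log-ratio below ln(0.1/15) = −5.011.

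**Conclusion.** The point holds in a conditional form. The stated rule yields zero for limits such as `<1`, `<0.1` and `<0.01`, and the planned log-ratio analyses have no readable provision for it. The realistic cases are TNF-alpha, IL-10, fasted insulin with HOMA-IR, and possibly post-baseline hsCRP.

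The effect runs from none to material. On the assumed distribution with a true change of −79.8%, the distortion is about 0.1 percentage point at a limit of 0.1 (−79.7%) and about 6 points at a limit of 1 (−73.7%). Both figures rest on invented assay limits and spreads and show range only.

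Neither a failure of the primary analysis nor any bearing on a formal secondary endpoint can be inferred. DAS28 (CRP) remains defined at zero, and the secondary endpoints in SAP 2.2.2 are adverse events and trough concentrations. This is a cheap improvement, not a threat to the trial's main conclusion.

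**What to change.** Add one sentence to SAP 4.3.7: for geometric summaries and log-scale models only, at baseline and post-baseline, a non-PK result below the limit is imputed as half the reported limit. Half the reported limit is the natural wording because 4.3.7 speaks of a detection limit, not an LLOQ, for non-PK data. For HOMA-IR, apply the substitution to insulin before the product is formed.

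State that the existing rule stays in force for all other uses, explicitly including the hsCRP value entering DAS28 (CRP), so that the primary endpoint is unchanged. Report the number of substituted values per arm and visit, so that a reader can see whether the convention matters.

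The cost is the sentence, a second analysis value for the affected markers and a count in the tables. The downside is the influence of single substituted values when the limit lies far below baseline, which the counts would expose.
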